3.7.5.7 Hyponatremia History

Each subject's hyponatremia medical history will be recorded at the baseline visit of the core safety follow-up component. The hyponatremia history should include the etiology of subject's hyponatremia and what treatment was administered before trial enrollment. Symptoms potentially attributable to hyponatremia should be specifically assessed for in prior history. The hyponatremia assessment at baseline will consist of documentation of hyponatremia etiology (eg, SIADH, hepatocellular disease [including cirrhosis], heart failure, or other) and prior hyponatremia treatment, ie, fluid restriction, if applicable. A detailed history specific to etiology of hyponatremia will also be recorded.

3.7.5.8 Clinical Status Assessment

Clinical status assessments will be performed per inpatient standard of care and should include review of patient chart entries, including hyponatremia assessment notes, trial- and nontrial-specific laboratory results, any examination findings, medical problem list changes, and fluid intake and output to evaluate overall subject eligibility in terms of hyponatremia state. The clinical assessment will focus on symptoms and signs which will inform treatment decisions (eg, the need to switch to rescue therapy, or the ability to safely discharge a subject from the hospital). The clinical assessment should be performed by a trial investigator who will be aware of laboratory and other clinical response data.

3.7.5.9 Vital Status

An assessment of vital status will be conducted on subjects who terminate prior to the Month 6 core safety visit, and do not withdraw consent for continued telephone contact. The telephone contact will be made on the date at which the subject would have reached the core safety follow-up component Month 6 visit (+ 2 weeks), and will be conducted with a reliable informant; either the subject and/or the parent/legal guardian, per investigator discretion. Vital status collected and recorded will be:

- Subject alive
- Subject deceased (date of death, cause of death)

3.7.6 Pharmacokinetic Assessments

3.7.6.1 Blood Collection Times

For subjects undergoing treatment with tolvaptan for at least 8 consecutive weeks (short interruptions of < 72 hours are still considered consecutive treatment), a single blood sample to measure tolvaptan and metabolite concentrations at steady state will be

obtained for each treatment cycle. The date and time of the PK sample and the date and time of the dose given immediately prior to the PK sample will be documented and recorded on the eCRF.

For each subject all samples will be collected according to local guidelines and best practices for pediatric care.

3.7.6.2 Sample Handling and Processing

All blood samples will be shipped to the testing facility for analysis. Specific information regarding sample handling and processing is provided in [Appendix 3](#).

3.7.7 End of Trial

The End of Trial Date is defined as the last date of contact or the date of final contact attempt from the Month 6 visit or early termination visit for the last subject completing or withdrawing from the trial.

3.7.8 Independent Data Monitoring Committee

An independent data monitoring committee (IDMC) has been established for this trial. This committee will meet on a regular basis to ensure the safe and ethical treatment of trial subjects, ensure the scientific integrity of the trial, and to ensure the trial is conducted within the bounds of ethical medical practice. It may make recommendations to the sponsor and trial steering committee to amend or terminate the trial based on grounds of safety, futility, or greater than expected efficacy as defined by the accepted statistical practices and procedures to be detailed in their charter. The specific duties of the IDMC will be detailed in a separate IDMC charter document.

3.8 Stopping Rules, Withdrawal Criteria and Procedures

3.8.1 Entire Trial or Treatment Component(s)

If the sponsor terminates or suspends the trial for safety or unanticipated other reasons, prompt notification will be given to investigators, IRBs/IECs, and regulatory authorities in accordance with regulatory requirements.

3.8.2 Individual Site

Individual trial site participation may be discontinued by the sponsor, the investigator, or the IRB/IEC if judged to be necessary for medical, safety, regulatory, ethical or other reasons consistent with applicable laws, regulations, and Good Clinical Practice (GCP). The investigator will notify the sponsor promptly if the trial is terminated by the investigator or the IRB/IEC at the site.

3.8.3 Individual Subject Discontinuation

If a subject discontinues from the trial prematurely, the reason must be fully evaluated and recorded appropriately in source documents and the eCRF. If the subject is being withdrawn because of an AE, that AE should be indicated as the reason for withdrawal.

All subjects have the right to withdraw at any point during the trial without prejudice. The investigator can discontinue a subject's participation in the trial at any time if medically necessary. In addition, subjects meeting the following criteria must be withdrawn from tolvaptan treatment:

- a) Occurrence of any AE, intercurrent illness, or abnormality in a laboratory assessment which, in the opinion of the investigator, warrants the subject's permanent withdrawal of tolvaptan treatment;
- b) Treatment with a prohibited concomitant medication other than the use of appropriate medications for the treatment of AEs under direction of the investigator;
- c) Subject noncompliance, defined as refusal or inability to adhere to the trial schedule or procedures (see [Section 3.12](#), Subject Compliance);
- d) At the request of the subject, investigator, Otsuka Pharmaceutical Development & Commercialization, Inc. (OPDC) or designee, or regulatory authority;
- e) Subject becomes pregnant; or
- f) Subject is lost to follow-up.

In addition, subjects on tolvaptan treatment who meet the following criteria should have results confirmed with a repeat test. Sodium tests should be done either STAT or through bedside monitoring.

- The subject's serum sodium increases by > 8 mEq/L (mmol/L) in any 10-hour period following dosing on Day 1 of a cycle
- The subject's serum sodium increases by ≥ 12 mEq/L (mmol/L) in the 24-hour period following dosing
- At any time after dosing, the subject's serum sodium is ≥ 145 mEq/L (mmol/L).
- Evidence of dehydration
- Abnormal liver function tests (see [Section 5.4](#))

If the result is confirmed, the medical monitor should be contacted to consider options of down-titration, dose discontinuation, concomitant medication adjustment, fluid supplementation, and/or withdrawal.

The sponsor and the medical monitor should be notified promptly when a subject requires IV normal saline or other rescue therapy. Subjects receiving rescue therapy are to continue to be monitored per protocol (to discharge or death). Subjects who have received rescue therapy secondary to inadequate response to tolvaptan will not be allowed to reinstate tolvaptan treatment.

The investigator will notify the sponsor promptly when a subject is withdrawn.

When a subject or parent/legal guardian or legally responsible representative decides to withdraw from the trial they will be asked to indicate whether they wish to discontinue from the trial as a whole, or still allow telephone contact. If they agree to continued telephone contact, they will be contacted at Month 6 for vital status ([Section 3.7.5.9](#)).

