3.1.1 Core Safety Follow-up Component

The core safety follow-up component of the trial is a 6-month period in which pediatric subjects (children and adolescents) with dilutional (euvolemic or hypervolemic) hyponatremia who previously participated in a tolvaptan hyponatremia trial will be followed (at a clinical trial site and/or through telephone calls), regardless of the need for treatment for hyponatremia, to assess the long-term safety of tolvaptan. There is no screening phase.

Enrollment into this trial should follow completion or discontinuation from the previous tolvaptan hyponatremia trial; the subject must have been off investigational medicinal product (IMP) for at least 7 days between trials. A longer lapse between completion of the previous tolvaptan hyponatremia trial and enrollment into this trial is permitted while enrollment is open.

The final laboratory assessments for liver function tests (LFTs) from the previous tolvaptan trial can serve as the baseline laboratory assessments for this trial if the values are within the normal range, and collected within 30 days of the baseline visit for this trial. However, LFTs for these subjects will be collected at Month 1 or Month 2 at a clinical site visit or local laboratory. If LFTs from the previous tolvaptan trial are abnormal, or collected > 30 days of the baseline visit of this trial, they will be assessed at baseline.

The last assessments in the previous tolvaptan trial will serve as the baseline assessments if collected within 30 days of enrollment into this trial. Otherwise, assessments will be repeated if > 30 days have lapsed since the previous tolvaptan trial.

Subjects enrolled in this trial will be assessed up to 7 times over the 6 month core safety follow-up component of the trial. The baseline and the Month 6/Early Termination (ET) visits are performed in the clinic, while assessments during Months 1, 2, 3, 4 and 5 will be conducted by telephone, unless LFTs are required at Month 1 or Month 2. During the in-clinic visits, subjects are evaluated for relevant trial information.

Baseline Visit

All subjects will attend the clinic for the baseline visit.

Months 1, 2, 3, 4 and 5

All subjects will receive telephone assessments for Months 1, 2, 3, 4, and 5. If LFTs are required at Month 1 or Month 2, the subject may obtain these results through a clinic visit or from a local laboratory.

Month 6/End of Trial Visit

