^g Vital status will be collected through telephone contact at Month 6 (+ 2 weeks) only for subjects who had an early termination and did not withdraw consent.

^h A full neurological examination will be completed at the baseline visit only if a full physical examination is performed (see footnote d).

ⁱ If > 30 days has lapsed since the previous tolvaptan trial, medications taken with 30 days of enrollment will be recorded.

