- 9) Body height and body weight will be measured.
- 10) Growth percentile will be calculated. Prior growth development information should also be collected, if available.

- 11) Tanner Staging will be transferred from the last assessments from the previous trial or completed as part of the physical examination, as appropriate. Historical staging information should also be collected, if available. A subject who has reached Stage 5 (both in pubic hair and genitalia) does not need to continue with Tanner Staging.
- 12) If the subject's last LFT (AST, ALT or BT) was abnormal or the subject's baseline visit occurred > 30 days after completion of the previous trial, the subject will be required to have LFTs assessed at baseline. If the subject's last LFTs were normal and the baseline visit occurred < 30 days after completion of the previous trial, LFTs will be collected at Month 1 or Month 2.
- 13) Quality of Life assessment will be performed, as appropriate by age and where available.
- 14) Concomitant medications will be recorded. If > 30 days have lapsed since the previous tolvaptan trial, medications taken within 30 days of enrollment will be recorded.
- 15) Adverse events will be assessed.

3.7.3.1.2 Months 1, 2, 3, 4, and 5

Subjects and/or their parents or legal guardians will be contacted by telephone at the end of Months 1, 2, 3, 4, and 5 (+ 2 weeks) to assess any new or ongoing AEs and to collect information on any medications administered since the last visit.

If the subject's last LFTs were normal and the baseline visit occurred < 30 days after completion of the previous trial, LFTs will be collected at Month 1 or Month 2 (in-clinic visit or local laboratory).

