3.7.3.1.3 Month 6/Early Termination

Subjects will return to the clinical trial site at the end of Month 6 (+ 2 weeks) or at early termination (ET) and the following assessments will be performed:

- 1) Any observable symptoms of hyponatremia will be assessed and recorded separately.
- 2) Vital signs (blood pressure, heart rate, respiratory rate, and temperature) will be assessed after the subject has been supine for ≥ 3 minutes. Vital signs should be performed prior to any blood draws.
- 3) A directed physical examination will be performed. Physical examination should include a fontanelle assessment as age appropriate.
- 4) Body height will be measured.
- 5) Body weight will be measured.
- 6) Growth percentile will be calculated.

- 7) Tanner Staging will be completed at the Month 6 clinical trial site visit or at ET according to the instructions specified in [Section 3.7.5.6](#) and [Appendix 4](#). A subject who has reached Stage 5 (both in pubic hair and genitalia) does not need to continue with Tanner Staging.
- 8) Quality of Life assessment will be performed, as appropriate by age and where available.
- 9) Concomitant medications will be recorded.
- 10) Adverse events will be assessed.

Month 6 is the completion visit, and subjects will no longer be eligible for optional tolvaptan treatment under this protocol at this time.

If a subject terminates early from the trial and agrees to continued telephone contact, the subject or parent/legal guardian will be contacted by telephone at Month 6 to assess vital status.

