5.7.3 Follow-up and Reporting of Serious Adverse Events Occurring After Last Scheduled Contact

Any new SAEs reported by the subject to the investigator that occur **after the last scheduled contact**, and are determined by the investigator to be reasonably associated with the use of tolvaptan, should be reported to INC Research. This may include SAEs that are captured on follow-up telephone call or at any other time point after the defined trial period (ie, up to last scheduled contact). The investigator should follow serious related AEs identified after the last scheduled contact until the events are resolved, stabilized, or the subject is lost to follow-up. The investigator should continue to report any significant follow-up information to INC Research up to the point the event has been resolved or stabilized.

6 Pharmacokinetic/Pharmacodynamic Analysis

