5.2.2 Adverse Events

Definitions:

- A treatment-emergent adverse event (TEAE) is an event that is observed or reported after administration of trial medication in this trial that was not present prior to trial medication administration or an event that represents the exacerbation of a pre-existing event. Exacerbation includes any event that increases in frequency or severity or becomes classified as serious after the start of treatment in this trial.
- An adverse withdrawal is a subject who withdrew from the trial due to an AE.
- A serious adverse event (SAE) is an AE that is classified as serious according to the criteria specified in the trial protocol.

The incidence of the following events will be summarized:

AEs and TEAEs

AEs and TEAEs by severity

TEAEs potentially causally related to the IMP

AEs and TEAEs with an outcome of death

Serious AEs and TEAEs

AEs and TEAEs leading to discontinuation

All AEs will be coded by MedDRA (Medical Dictionary for Regulatory Activities) system organ class and preferred term.

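### The Month 6 call to early leavers records only vital status, so new non-serious AEs after exit and new SAEs beyond 14 days are not sought

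*Protocol*

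**What the plan says.** Children who stay in the core component are followed mainly by telephone. Protocol Section 3.1.1 states that "assessments during Months 1, 2, 3, 4 and 5 will be conducted by telephone", unless liver tests are due at Month 1 or 2. Section 3.7.3.1.2 gives the purpose of those calls: "to assess any new or ongoing AEs and to collect information on any medications administered since the last visit".

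For a child who leaves early, four places agree.

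- Section 3.8.3 asks the family whether they are leaving altogether or will still accept calls. For the second group: "If they agree to continued telephone contact, they will be contacted at Month 6 for vital status".
- Section 3.7.3.1.3 says that the subject or parent is "contacted by telephone at Month 6 to assess vital status".
- A footnote to the core schedule (Table 3.7.1-1) says: "Vital status will be collected through telephone contact at Month 6 (+ 2 weeks) only for subjects who had an early termination", provided consent was not withdrawn.
- Section 3.7.5.9 says: "An assessment of vital status will be conducted on subjects who terminate prior to the Month 6 core safety visit". It lists two possible records: alive, or deceased with date and cause. There is no AE, hospitalisation or medication item.

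The objective (Section 2.3) is six months of safety follow-up, and Section 3.3.1 applies this to all subjects whatever their treatment. Section 7.4.2 makes the frequency of AE reports a secondary endpoint for all enrolled subjects.

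**The concern.** The protocol already collects AEs by telephone and already plans a Month 6 call to these families, but asks nothing about AEs on it. A new hospitalisation in Month 4, in a child who left at Month 2, would not be asked about.

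These children remain in the Core Dataset, which is everyone with a signed consent form (SAP Section 5.1.1). SAP Section 5.2.2 summarises AE incidence and describes no adjustment for follow-up time. Time in which nobody asked about events therefore counts as event-free time, and crude six-month incidence is biased downwards. The rationale given for the vital-status call in the Amendment 3 summary is to verify safety through the expected six months. A survival record meets that aim only in part.

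**Working it through.** **1. What remains after early termination**

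| Provision | Covers | Does not cover |
|---|---|---|
| ET visit (3.7.3.1.3) | AEs up to that visit | Anything later |
| 5.7, AE follow-up | Two weeks after the Month 6 visit | A leaver, who has no such visit |
| 5.7.2, SAE monitoring | SAEs for 14 days after ET (or after last dose, if later) | New SAEs beyond that |
| 5.7.1 and 5.7.2, open events | AEs and SAEs already identified, to resolution or stability | New events |
| 5.7.3, later SAEs | Those the subject reports and that "are determined by the investigator to be reasonably associated with the use of tolvaptan" | Unrelated or unreported SAEs; all non-serious AEs |
| Month 6 call (3.7.5.9) | Survival, date and cause of death | Every other event |

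The gap is new non-serious AEs after ET, and new SAEs beyond 14 days that are unrelated or not volunteered.

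**2. Length of the gap by month of exit**

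For exit just after the Month k contact, the AE telephone calls forgone number 5 − k. The months with no question about new AEs number 6 − k. The months without SAE monitoring are 6 − k − 14/30.4.

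| Exit month k | AE calls forgone | Months, new AEs not sought | Months, no SAE monitoring |
|---|---|---|---|
| 0 | 5 | 6 | 5.54 |
| 1 | 4 | 5 | 4.54 |
| 2 | 3 | 4 | 3.54 |
| 3 | 2 | 3 | 2.54 |
| 4 | 1 | 2 | 1.54 |
| 5 | 0 | 1 | 0.54 |

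**3. Trial-level size**

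The plan has no figure to reproduce: about 100 subjects is an expectation (Protocol Section 7.1), and no dropout rate is given. Assumptions: N = 100, dropout proportion d, and exit uniform over 0 to 6 months, so that a leaver loses 3 months on average. Person-months lost = 100 × d × 3, out of 600.

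**4. Effect on crude incidence**

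Let r be the true six-month risk, the same in leavers and stayers, with constant hazard λ = −ln(1 − r)/6. A leaver's mean observed risk is 1 − r/(6λ).

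- r = 0.30: 6λ = 0.3567, and 1 − 0.30/0.3567 = 0.159.
- r = 0.10: 6λ = 0.1054, and 1 − 0.10/0.1054 = 0.051.

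Observed incidence = (1 − d) × r + d × leaver risk. For r = 0.30 and d = 0.20 this is 0.80 × 0.30 + 0.20 × 0.159 = 0.272.

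| Dropout d | Person-months lost | Share of 600 | True 30% reads as | True 10% reads as |
|---|---|---|---|---|
| 5% | 15 | 2.5% | 29.3% | 9.8% |
| 10% | 30 | 5% | 28.6% | 9.5% |
| 20% | 60 | 10% | 27.2% | 9.0% |
| 30% | 90 | 15% | 25.8% | 8.5% |

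The person-time losses are upper limits on what a changed call could recover. They assume that every leaver accepts calls, and they do not subtract the 14-day SAE window.

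**5. A death first learned at the Month 6 call**

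Death is an SAE outcome (Section 5.1). Section 5.7.2 sends SAEs identified at the last scheduled contact to the AE form, with no relatedness condition. Section 5.7.3 covers new SAEs after that contact and requires relatedness. Which rule applies depends on whether the vital-status call is the last scheduled contact, and that term is not defined. The SAP has no vital-status table. Its death summary, "AEs and TEAEs with an outcome of death", counts only deaths recorded as AEs.

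**The case against.** **Not everything is lost.** A reader might infer that a leaver's AEs disappear altogether. They do not: a child who leaves with an open AE is contacted at least every four weeks until it resolves or is stable (Section 5.7.1), and SAEs are followed to resolution or stability (Section 5.7.2). A child who only stops tolvaptan stays in core follow-up to Month 6 (Section 3.7.3.2.7.3) and is unaffected. This stands, and it limits the gap to new events.

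**Deaths are probably counted already.** A reader might infer that deaths known to the sponsor will be missing from the death table. The documents do not establish this. The Month 6 call is scheduled for early leavers, so Section 5.7.2 can be read as requiring AE entry. What stands is an undefined term that one sentence would settle.

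**Keeping the monthly calls would undo the withdrawal.** A reader might infer that the Month 1 to 5 calls should continue for these families and would recover nearly all the loss. But between baseline and Month 6 the core component consists of those calls plus at most one liver-test draw. A family content to take them could have stayed enrolled, so wide acceptance cannot be assumed. Amendment 3 also set out to reduce burden. This stands, and it leaves the single existing call as the sensible place to act.

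**Informative dropout is not shown.** That sicker children leave more often is plausible, but nothing in the documents says so. The calculation above assumes equal risk.

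**Consent.** Whether agreement to telephone contact covers AE and medication data cannot be judged from these documents.

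**Conclusion.** The gap is real but limited. For early leavers who accept telephone contact, the plan has no step that elicits new non-serious AEs after ET or new SAEs beyond 14 days, and the one later call omits the question.

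With uniform exit, at most about 5% of AE-observed person-time is lost at 10% dropout and 10% at 20%. Under equal risk and constant hazard, a true 30% incidence would read as 28.6% and 27.2% respectively. A reader might infer a larger loss by assuming earlier exits: a mean exit at Month 2 gives 0.20 × 4/6 = 13% at 20% dropout. The documents support neither that timing nor any particular dropout rate.

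The passages on the call agree with each other, so this is a design weakness and not a contradiction. It merits a grade between optional and recommended, with moderate confidence. SAP Section 5.1 reports early termination of the trial, which limits what a protocol change can still achieve here.

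**What to change.** 1. In Protocol Sections 3.7.5.9, 3.7.3.1.3 and 3.8.3, and the matching footnote to Table 3.7.1-1, have the existing Month 6 call also ask about AEs and SAEs, hospitalisation and hyponatremia treatment since the last contact. Use the existing AE and medication forms, with consent wording to match.
2. In Section 5.7.2, state that this call is a scheduled contact, so that a death learned there is entered as an AE whatever its relatedness.
3. In SAP Section 5.2.2, add one line saying that deaths from the vital-status record are included in the death summary. This is the part most readily applied now.
4. Optionally, offer the remaining Month 1 to 5 calls to families who want them. This is not required.

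No visit or procedure is added. The cost is a few minutes per call, some wording changes, and a recall period that can run to several months. Recall over that period should serve hospitalisations and serious events better than minor AEs, so the call would not recover all of the lost information.
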